3.0	06/24/2024	
 1) Updated "[name]" with "[name]" (name and contact info) 2) Updated qualitative retention interview inclusion criteria 3) Updates and additions were made to the qualitative retention interview portion of the interview guide 	
 1) [name] has replaced [name] as research coordinator of the study. 2) We expanded our inclusion criteria and anticipated number of participants for the retention interviews so that we could include key informants from the clinic level, such as administrators. 3) We made some edits/additions after review of the first few retention interviews conducted with patient participants.
3.1	08/28/2024	Increased the number of healthcare worker (HCW) participants and patient participants for qualitative retention interviews by 1 each	A HCW that we'd like to interview was out on medical leave when we were recruiting; she has since returned to work and got back to us expressing interest in participating (and we have the funds to cover additional interviews). We are also increasing our maximum patient participants by one.
4.0	10/14/2024	Changed reimbursement method to Advarra, added patient information letter as a new retention strategy, added qualitative questions to see what patients thought about the new letter	UW policy is mandating switching to Advarra for study reimbursements as of 01/01/2025; initial qualitative interviews of patients suggested we should add a letter to serve as a reminder about the goals of the study and what to expect
5.0	02/06/2025	Updated ratio of active patients to historical controls & removed the date constraint for historical controls; removed [name]'s work phone number	
Per our statistician, with our final number of active patients, we need 135 historical controls for 80% power. We have exhausted our options within the date constraint initially included due to COVID. We think it's more important to be adequately powered and will include COVID as a limitation.
 
[name] will no longer have a dedicated UW number as of 2/28/25

2.0 LIST OF ABBREVIATIONS

AE	Adverse Event
BAA	Business Associate Agreement
CCC	Clinical Coordinating Center
CFR	Code of Federal Regulations
CHDR	The Center for Health Disparities Research
CMP	Clinical Monitoring Plan
Cooperative	Rural Wisconsin Health Cooperative
CRF	Case Report Form
CTCAE	Common Terminology Criteria for Adverse Events
CTMS	Clinical Trial Management Software
DCC	Data Coordinating Center
DHHS	Department of Health and Human Services
DMC	Data Monitoring Committee
DSMB	Data & Safety Monitoring Board
DSMC	Data & Safety Monitoring Committee
DSMP	Data & Safety Monitoring Plan
eCRF	Electronic Case Report Forms
EDC	Electronic Data Capture
GCP	Good Clinical Practice
HIP	Health Innovation Program
HIPAA	Health Insurance Portability and Accountability Act
ICTR	Institute for Clinical and Translational Research
IND	Investigational New Drug Application
IRB	Institutional Review Board
IT	Information Technology
MOP	Manual of Procedures
NIH	National Institutes of Health
OHRP	Office for Human Research Protections
OnCore	Online Collaborative Research Environment
PCP	Primary Care Provider
PHI	Protected Health Information
PI	Principal Investigator
POC	Point of Contact
REDCap	Research Electronic Data Capture
SAE	Serious Adverse Event
SAP	Statistical Analysis Plan
sIRB	single IRB
SMART IRB	Streamlined, Multisite, Accelerated Resources for Trials IRB
SMC	Safety Monitoring Committee
SMPH	School of Medicine and Public Health
SPH	Sauk Prairie Healthcare
UP	Unanticipated Problem

3.0 STUDY SUMMARY

[figure not shown]
3.1 Synopsis

Full Title	Crossing the Divide: Piloting an Integrated Care Model to Bridge Rural-Urban Healthcare Systems and Reduce Major Amputations Among Rural Patients with Diabetic Foot Ulcers
Short Title	Crossing the Divide
Protocol Number	2022-1338-CP
ClinicalTrials.gov Identifier & Summary	NCT05203471 This study is being done to pilot an integrated care model that focuses on improving collaboration between rural primary care providers and urban specialists, particularly infectious disease physicians and vascular surgeons
Number of Sites	This is a single site study conducted in the United States. A total of 3 clinics serving rural Wisconsin with preference for those participating in the Rural Wisconsin Health Cooperative will be identified. Attempts will be made to select one clinic each from a rural advantaged, rural, and rural disadvantaged community.
Main Inclusion Criteria	
Healthcare Workers:
 
 Rural providers (primary care providers at UW Health Belleville and wound care and diabetes care specialists at Sauk Prairie Healthcare) and schedulers placing referrals Employment at a rural advantaged, rural, or rural disadvantaged community clinic selected for participation 
Patient Participants:
 
 Participating rural provider Diabetic foot ulcer diagnosis
Main Exclusion Criteria	
Healthcare Workers:
 
 Insufficient overlap in work schedules between rural providers and schedulers 
Patient Participants:
 
 Receiving palliative care No insurance to cover referral to University of Wisconsin Specialty Clinics
Objective(s)	
Primary Objectives
 
 Evaluate the potential of our integrated care model to reduce major amputations by examining its impact on guideline-concordant care processes, including urban specialty referral Build recruitment and retention strategies for the trial that work across diverse, rural clinics
Endpoints	
Primary Endpoints
 
 Completion of 5 vascular and 4 infectious disease care processes, modeled as percent indicated and dichotomously (all relevant completed vs. missing ≥ 1) Development and refinement of recruitment and retention strategies that meet our goal targets of 60% and 80%, respectively 
Secondary Endpoints
 
 Amputation, either major or minor, within 3 months of follow-up

[figure not shown]
Study Design	This is a phase II pre-post serial cohort design trial with adaptive recruitment and retention strategies. Enrollment will be implemented in two phases; healthcare systems will be enrolled in consecutive 6-month periods.
Study Intervention	A rural integrated care model consisting of a care algorithm for use by rural primary care providers to guide integrated care for patients with diabetic foot ulcers, and a referral checklist for use by rural schedulers to place referrals with urban specialists.
Total Number of Subjects	Up to 45 patient participants will be enrolled in the study with additional historical control patients obtained via chart review (1 active patient participant; 5 historical control patients, up to 180 patients total). Up to 30 healthcare workers will be enrolled (180+30=210 individuals participating in the care algorithm pilot). From the pool of patients and healthcare workers approached for recruitment, we will ask up to 36 individuals, consisting of 18 patient participants and 18 healthcare worker participants, to participate in feedback interviews; this group will be a mix of both those that enrolled in the integrated care intervention study and those that declined participation in the study. These individuals will provide qualitative data needed to build recruitment and retention strategies, meeting our second objective. We are uncertain of the exact mix of qualitative participants who will have consented or not to participate in the care algorithm pilot. Therefore, the total number of subjects is anticipated to be between 190 and 246, including historical controls.
Study Population	Patient participants are adults aged 18+ diagnosed with diabetic foot ulcers and receiving care at a participating clinic. Health workers include primary care providers, other healthcare providers such as specialists, and schedulers employed at a participating clinic.
Statistical Methodology	Although this sample size is not powered to detect differences in major amputation, it does provide adequate power to find a difference in care processes proximal to major amputations. With a fixed sample size of 27 active patients, matched 1:5 pre/post with historical controls, alpha of 0.05, we are powered at >0.90 to detect an absolute increase of 30% (from 20% to 50% completion, measured dichotomously) in the group receiving integrated care.
Estimated Subject Duration	The duration of the study for each patient participant is approximately 3 months.
Estimated Enrollment Period & Study Duration	Study enrollment and follow-up will occur over 24 months with the total expected duration of the trial to be 36 months.

3.2 Schematic of Study Design

Phase II pre-post serial cohort design schematic to test the rural integrated care model

Adaptive recruitment & retention study design to build recruitment & retention strategies that work across diverse, rural clinics

5.0 INTRODUCTION

5.1 Disease Background

Over two million Americans develop a diabetic foot ulcer each year, costing >\$1.3 billion.^{1,2} While other diabetes complications are decreasing, the CDC estimates that, since 2009, all diabetes-related amputations have increased 63%.^{3,4} Above-ankle, major amputations increased 29% — the worst rates in more than 20 years.^{3,5} The impact is unquestioned: patients with diabetic foot ulcers fear major amputation more than death.⁶ Six million patients living with diabetes in rural areas have even poorer outcomes.⁷

Our team and others found that rural patients have 37% higher odds of major amputation and 40% higher odds of premature death than their urban counterparts, even after controlling for other sociodemographics, ulcer severity, and comorbidities.^{8,9} Furthermore, baseline rates of diabetes and other amputation risk factors, like smoking, are higher in rural populations compared to urban; these rates are rising in the wake of the COVID-19 pandemic.^{7,10-14} We urgently need interventions to assist rural healthcare teams in caring for these high-risk, rural patients with diabetic foot ulcers.

5.2 Current Standard of Care

Many urban, tertiary care centers have decreased the risk of major amputation and death by approximately 40% after implementing integrated care models that focus on centralizing multiple specialists into a single clinic to facilitate side-by-side collaboration.¹⁵ Urban integrated care models work by co-locating multiple specialists in the same clinic and using algorithms to address four physiologic factors: 1) poor glycemic control, 2) vascular disease, 3) mechanical complications, and 4) secondary infection. However, the urban integrated care model has never been adapted to rural, primary care settings until our team partnered with the Rural Wisconsin Health Cooperative to design such a model. The current work aims to pilot our integrated care model for the first time in preparation for a statewide clinical trial of its effectiveness.

5.3 Integrated Care Model to Reduce Amputations from Diabetic Foot Ulcers in Rural Clinics

Our integrated care model promotes cross-setting collaboration without co-location through the utilization of two tools: 1) a care algorithm and 2) a referral checklist. The care algorithm supports rural primary care in providing high quality, local care to most patients. It also addresses obstacles to collaborating with urban specialists by providing *a priori* agreed upon referral criteria including timeframes, clinical indications, and pre-consultation diagnostics for severe disease. The referral checklist will support rural clinic schedulers, who place referrals to urban specialty clinics, by providing schedulers with a list of documents that should be included, reducing barriers of time-consuming triage and disjointed electronic health records.

5.4 Rationale

5.4.1 Integrated Care Model

Adapting the urban model of integrated care to rural settings is a highly promising solution to overcome rural disparities in major amputations. Our systematic review of 33 studies found that integrated care reduces major amputation and death for patients with diabetic foot ulcers by approximately 40%.¹⁵ It uses a coordinated, systematic approach to address four physiologic factors: 1) poor glycemic control, 2) vascular disease, 3) mechanical complications, and 4) secondary infection. Multi-specialist teams average five disciplines and rely on co-location, urban referral pathways, and care algorithms to guide care for shared patients.¹⁵ Multiple professional societies recommend integrated care for patients with diabetic foot ulcers.^{16,17} These models have been successfully implemented in major cities spanning four continents.¹⁵ However, integrated care models have never been adapted to rural settings, where co-location with multiple specialists is not feasible.

Among rural patients, poor collaboration with specialists accounts for 55% of excess hospitalizations and 40% of excess mortality, compared to urban residents.¹⁸ This is most salient for high-risk patients requiring vascular surgery or infectious disease input, who face a 90-fold increased risk of major amputation.¹⁹ Using a national Medicare sample of 56,440 patients with diabetic foot ulcers, our team reported that infectious disease physicians are associated with a reduced risk of major amputations (HR 0.83, p<0.001).²⁰ Others found that vascular surgeons are associated with a 38% reduction in major amputations.²¹ However, both specialties almost exclusively practice in urban settings.²² For rural patients to receive integrated care including input from these limb salvage specialists, teams must collaborate across the rural-urban health system divide.²³

Our qualitative research highlights that, without a systematic way to provide integrated care, rural healthcare teams struggle to collaborate with urban specialists.^{23,24} Our analysis of 44 interviews with rural patients, their caregivers, and healthcare workers emphasized the impact of delayed, poorly coordinated care with urban specialists. Rural-urban healthcare worker collaborations are stymied by: 1) time-consuming referrals, 2) negative interactions, and 3) multiple, disjointed electronic health records.²³

In preliminary work, our team, in partnership with the Rural Wisconsin Health Cooperative (Cooperative), developed an intervention to address this critical gap. The Cooperative is a nationally recognized consortium of 43 rural health systems throughout the state dedicated to improving rural diabetes care. Together, we co-designed the first integrated care model adapted to the rural setting that promotes collaboration across the rural-urban divide.^{23,24} The model streamlines the referral process and overcomes disjointed electronic health records by providing a checklist to be used by rural support staff (clinic schedulers) when faxing critical triage information between clinics. It establishes *a priori*, mutually agreed-upon criteria for timely, urban specialty referrals. We hypothesize that our rural integrated care model will reduce major amputations for rural patients with diabetic foot ulcers. Our hypothesis is based upon 1) implementing a model that directly addresses the most pressing health system barriers identified in our prior work, 2) the documented success of urban integrated care, and 3) the strength of our partnership with rural stakeholders in the co-design and pilot phases of our research.^{25,26}

5.4.2 Recruitment and Retention Strategies

Inadequate recruitment and retention into clinical trials are the two top reasons clinical trials fail.²⁷ Furthermore, rural participants are under-represented in clinical trials, and there is a paucity of data regarding how to improve rural participation.^{28,29} Therefore, it is critical that we develop strong recruitment and retention strategies during this pilot to assure subsequent trial success. We will collect quantitative data on the number of recruited patients and 3-month retention over the pilot. To improve these metrics, we will analyze qualitative data from healthcare workers and patients using an existing conceptual model of participant-centered recruitment and retention.³⁰ Our 2-wave, adaptive design allows us to pilot two iterations of recruitment and retention strategies. Adaptations will be co-designed with the Cooperative prior to activating the second and third clinics and upon completion of the pilot. Using qualitative data to drive improvements in recruitment and retention is a proven approach.^{31,32} In one instance, recruitment rates nearly doubled from 35% at the beginning of the pilot to 69% during the definitive trial.³¹⁻³³ Our goal is to develop strategies that achieve a recruitment rate of 60% and retention rate of 80%, which would place us in the top tertile of clinical trial performance and ensure an adequately powered statewide trial.^{34,35}

6.0 STUDY OBJECTIVES AND ENDPOINTS

Objectives	Endpoints
Primary	

Evaluate the potential of our integrated care model to reduce major amputations by examining its impact on guideline-concordant care processes, including urban specialty referral	A) Completion of 5 vascular and 4 infectious disease care processes, modeled as percent indicated and dichotomously (all relevant completed vs. missing ≥ 1) B) Amputation, either major or minor, within 3-month follow-up
Build recruitment and retention strategies for the trial that work across diverse, rural clinics	Development and refinement of recruitment and retention strategies that meet our goal targets of 60% and 80%, respectively

7.0 STUDY DESIGN

7.1 General Design

This is a phase II pilot of an integrated care model for treatment of diabetic foot ulcers in rural patient populations and includes adaptive recruitment and retention strategies. The protocol uses a pre-post serial cohort design, where the second and third clinics are activated six months after the first clinic and all clinics complete the trial simultaneously. This design allows: 1) use of refined recruitment and retention strategies when the final two clinics are activated, and 2) dispersion of activation efforts to facilitate completion by small research teams. Subject accrual will occur over 24 months. The design was modified so that clinics 2 and 3 could be activated simultaneously based on 1) our 100% recruitment of healthcare workers from clinic 1, which was greater than expected, and 2) our lower than expected patient recruitment from clinic 1. Having the third clinic activated for longer than initially planned should increase our likelihood of recruiting enough patients into the trial.

The study population will consist of 45 patient participants that develop diabetic foot ulcers during the enrollment period and receive care from participating rural providers (primary care providers (PCPs) at UW Health Belleville and diabetes or wound care providers at Sauk Prairie Healthcare) at rural clinics taking part in the study. Clinic schedulers, in addition to rural providers, will also be enrolled. Patient participants will be eligible only if their rural provider already consented and enrolled in the study. Patient participants will complete screening activities and their rural provider(s) and clinic scheduler will use the integrated care model to assist with care decisions (although rural providers will retain clinic discretion to deviate from the integrated care model to best serve the patient). Study activities include screening, chart reviews, and telephone assessments. Historical control data from up to 180 patients (1:5 active patient enrollment: historical control matching) will be obtained from medical records for comparison. Historical controls will be matched based on clinic and providers but no other factors due to the low overall volume of patients on any one provider's panel with diabetic foot ulcers.

Recruitment and retention strategies will be adapted iteratively during the study. Prior to enrollment of clinics 2 and 3, we will meet with administration and key healthcare workers from SPH to share our qualitative recruitment results from clinic 1 (Belleville) and brainstorm modifications that hold promise for successful recruitment of healthcare workers and patients at SPH's clinics 2 and 3. Data on recruitment and retention will be obtained through interviews with a subset of healthcare workers (e.g., rural providers, schedulers, and administrators) and patient participants, and through tracking of recruitment and retention efforts.

7.2 End of Study Definition

The end of the study is defined as the date of completion of any final follow-up activity or data collection described in the protocol.

8.0 SUBJECT SELECTION

8.1 Inclusion & Exclusion Criteria

8.1.1 Healthcare Workers

Inclusion Criteria

1. Willing to provide informed consent.
2. Willing to comply with study procedures
3. Rural providers (PCPs in Belleville; diabetes and wound care specialists in SPH) and schedulers placing referrals.
4. Employed at a participating rural clinic.
5. For rural providers, confirm understanding that they will retain clinical discretion to deviate from the integrated care model if they think it would best serve the patient.
6. Available for the duration of the study.

Exclusion Criteria

1. Insufficient overlap in work schedules between rural provider and scheduler based on clinic manager determination.

8.1.2 Patients (including Historical Controls)

Eligibility will be determined by inclusion and exclusion criteria below and confirmed by medical record review as necessary.

Inclusion Criteria

1. Able and willing to provide informed consent.
2. Willing to comply with study procedures and be available for the duration of the study.
3. 18 years of age and older.
4. Patient with either type 1 or type 2 diabetes at a participating rural clinic.
5. Develops diabetic foot ulcer during enrollment period.

Exclusion Criteria

1. Receiving palliative care such that referral to urban centers for aggressive limb salvage would be inappropriate (as assessed by their rural provider).
2. Insurance would not cover referral to the University of Wisconsin specialty clinic.
3. Not suitable for study participation due to other reasons at the discretion of the investigators.

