10.2.2.3 Baseline Visit and Enrollment

Following informed consent, subject eligibility will be confirmed as follows:

A patient participant will be defined as "enrolled" in the study when they meet the following criteria:

- The patient participant has been consented by a research coordinator.
- The patient participant and a research coordinator have completed all screening documentation.
- The PI has verified that the patient participant meets all of the inclusion criteria.
- The PI has verified that patient participant meets none of the exclusion criteria.
- The patient participant completed a clinic visit with the participating rural provider, who considered recommendations outlined in the integrated care algorithm.

Following enrollment, the participant's medical record will be reviewed, and patient characteristic data will be abstracted. This will include sociodemographic data, comorbidities, medications, lab values, and ulcer characteristics. See Appendix for full list of variables.

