10.3 Historical Control Patient Participants

10.3.1 Screening and Enrollment

Controls will be matched 1:5 with enrolled patient participants based on clinic and primary care provider and identified through a review of medical records. Additionally, CRDS will be used to screen for historical controls at the UW Health Family Medicine Clinic in Belleville, and data will be delivered to the study team through REDCap. Controls will be identified and selected starting from the date 3 months prior to clinic activation and going back in time until the required number is reached. . The 3-month wash-out will avoid contaminating primary care teams with intervention activation events. Patients receiving palliative care, those unable to provide consent, and those who lacked insurance covering referral to University of Wisconsin specialty clinics will be excluded from the control population consistent with prospectively enrolled patient participants.

A waiver of informed consent and HIPAA authorization waiver has been obtained for data abstraction activities for historical controls. This aspect of the study meets the four criteria for a waiver of HIPAA authorization. First, the research involves no more than minimal risk to the historical controls as it consists of a chart review only. Second, the research could not practicably be carried out without the

waiver since a substantial proportion of the historical controls are likely to have died (~20% in our national cohort study were dead within one year). Third, the research could not practically be carried out without using Identifiable Private Information because we need to access their medical records, which contain the most accurate record of what care they received for their foot ulcer. Fourth, the waiver is unlikely to adversely affect the rights and welfare of the subjects due to the procedures we have in place to maintain the confidentiality of all participants, both historical and prospective.

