12.0 DATA HANDLING AND RECORD KEEPING

12.1 Data Collection

12.1.1 Data Collection

Standardized data collection forms (e.g., source documents, case report forms, standardized assessment forms, etc.) are used to ensure data collected are consistent and compliant with the protocol and IRB application.

Data collection is the responsibility of the research coordinators under the supervision of the Principal Investigator (PI). The PI is responsible for ensuring the accuracy, completeness, legibility, and timeliness of the recorded and reported data.

All data collection forms must be completed in a legible manner; any missing data will be explained. Data entry errors will be corrected with a single line through the incorrect entry and the correct data is entered above/near the correction. All changes will be initialed and dated. Forms will be filled out electronically or using black or blue ink.

Data collection forms are maintained in the subject files and retained as described in Section 12.3: Records Retention.

Data collection will be done through manual chart abstraction by [name], [name], and/or [name]. These individuals will be granted remote access to all three clinics' electronic medical record. A business associate agreement (BAA) with SPH will be put in place for this purpose. A unique study ID will be assigned to each patient participant. A key linking the patient participant's ID and the study ID will be kept on the HIPAA compliant HIP server and UW Restricted ResearchDrive. A coded dataset will be created on the HIP servers/UW Restricted ResearchDrive and REDCap for analytic purposes and ICTR DMC oversight purposes.

Study data will be documented and monitored in SMPH REDCap. Data will be collected on paper as described above, recorded by either the study participant or research staff, then electronically entered, with confirmation of correct entry, by the research staff via REDCap on research computers. To gain access to the REDCap system, study team members will need to fill out a REDCap account request through ICTR and complete required training using the following link:

<https://redcap.ictr.wisc.edu/surveys/?s=DWJFCLFHYL8PKJRT>

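### The open discretionary exclusion in 8.1.2 appears to apply to historical controls, who are picked from charts that already show the outcome

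*Combined protocol and SAP*

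**What the plan says.** The heading of section 8.1.2 says that its criteria include historical controls. The text below it adds: "Eligibility will be determined by inclusion and exclusion criteria below and confirmed by medical record review as necessary". The third exclusion covers anyone "Not suitable for study participation due to other reasons at the discretion of the investigators", with no listed reasons, no time limit and no requirement to record its use.

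Section 10.3.1 sets out how controls are found. Selection starts three months before clinic activation, "going back in time until the required number is reached". On exclusions it says: "Patients receiving palliative care, those unable to provide consent, and those who lacked insurance covering referral to University of Wisconsin specialty clinics will be excluded". It describes this as consistent with the prospective patients, but exclusion 3 is not in the list.

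Section 10.3.2 and Appendix 10 then take baseline and 3-month data, care processes, amputation and death from the same records. Under 13.1 a patient counts as a completer only if every relevant process was done. Section 13.2 fixes the comparison at 27 active patients with five controls each.

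**The concern.** An open suitability clause is common in trials where eligibility is settled before the outcome exists. Here, for controls, it is not. Whoever decides whether a control is suitable has a finished chart that holds the care to be scored, and no passage restricts which entries may be read or separates that decision from abstraction. Because selection continues until the number is filled, dropping one control brings in another and leaves no gap in the final count.

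Working backwards in date order protects against picking and choosing only if nobody can be skipped on judgement. Exclusion 3, if it applies, permits skipping. Suitability to take part also has little meaning for a person whose chart alone is used under a consent waiver.

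At stake is the control completion rate, on which both forms of the primary endpoint depend, and the amputation comparison. Matching on clinic and provider would not correct selection of this kind, and 13.2 has no analysis that restores excluded patients.

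**Working it through.** **Which list governs controls**

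| Point | 8.1.2 | 10.3.1 |
|---|---|---|
| Applies to controls | Yes, by its heading | Yes, it is the control procedure |
| Palliative care | Excluded | Excluded |
| Insurance not covering referral | Excluded | Excluded |
| Unable to consent | Through the inclusion criteria | Excluded |
| Investigator discretion | Excluded | Not mentioned |

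The lists differ on the last row, and no passage says which prevails.

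**What is visible when a control is judged.** A control's baseline lies at least three months before clinic activation, so the 3-month window has closed before selection begins. All scored items, amputation and death can be in the chart.

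**Size, as an illustration.** The plan gives no figure for discretionary exclusions. Its power figure confirms the design used below: the matched case-control formula with 27 sets, 5 controls each, control exposure 0.6, correlation 0.3, odds ratio 0.26 and two-sided 0.05 gives 0.803, against the stated 0.80706.

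Inputs: 27 active and 27 × 5 = 135 controls (13.2); 20% completion (synopsis), taken as true in both arms, so there is no real effect. The share *r* of control completers passed over is assumed to be 0.1 or 0.2.

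Control completion after removal = p(1 − r) / [p(1 − r) + (1 − p)].

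- r = 0.1: 0.18 / (0.18 + 0.80) = 18.4%; ratio of active to control 20 / 18.4 = 1.09.
- r = 0.2: 0.16 / (0.16 + 0.80) = 16.7%; ratio 20 / 16.7 = 1.20.

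Controls passed over while filling 135 places = 135 / (1 − p·r) − 135.

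- r = 0.1: 135 / 0.98 − 135 = 2.8, about 3 charts.
- r = 0.2: 135 / 0.96 − 135 = 5.6, about 6 charts.

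False positives: sum the binomial probabilities over all pairs of counts for which the pooled two-sided z test at 0.05 is significant in favour of the model.

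| Control completers passed over | Active v control completion | False positives favouring the model |
|---|---|---|
| None | 20% v 20% | 3.0% |
| 1 in 10 | 20% v 18.4% | 4.8% |
| 2 in 10 | 20% v 16.7% | 7.7% |

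If the 0.6 in 13.2 means missing at least one process, completion would be 40%. The same steps give control rates of 0.36 / 0.96 = 37.5% and 0.32 / 0.92 = 34.8%, and false positives rise from 2.7% to 4.6% or 7.9%. The result depends little on which rate is used.

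**The case against.** The best reply is that 10.3.1 is the specific procedure and should prevail. The 8.1.2 list cannot be applied word for word to controls, since it also asks for willingness to consent and an ulcer arising during enrolment. On that view the conflict is a drafting mismatch. The documents also suggest pressure to keep controls: provider volumes are low (7.1), and the revision history says the eligible charts within the former date limit had been exhausted. This is a fair reading and a reason to expect little use of the clause. It does not settle the matter, because the 8.1.2 heading names controls explicitly and no log would show whether anyone was skipped.

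A second reply is that the scenarios assume removal fully aligned with the endpoint. That is so. Removal unrelated to care would cause no bias of this kind, and removal of non-completers would work against the model.

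A reader might extend the concern equally to the active arm. Section 10.2.2.3 makes enrolment depend both on the check that "The PI has verified that patient participant meets none of the exclusion criteria" and on a further condition: "The patient participant completed a clinic visit with the participating rural provider, who considered recommendations outlined in the integrated care algorithm". Section 10.2.2.2 also places the consent discussion after the clinic visit. The order is therefore blurred, but the documents do not support the stronger reading:

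- Eligibility is discussed with the provider before the telephone call (8.4.2) and screened by telephone, with the reason for ineligibility recorded (Appendix 5).
- The calendar in 10.2.1 puts eligibility at the baseline visit, ahead of the intervention column, and 10.2.3.1 puts model activities after enrolment.
- At that visit the 1-week, 2-week and 3-month items and any later amputation are still unknown. Only baseline items could be in view.
- The logs in 11.2 and 11.3.2 count consented patients, which bounds any removal after consent. Losing 2 in 10 non-completers at 20% completion would mean 27 / (1 − 0.8 × 0.2) = 32 patients consented for 27 kept, a gap of about 5 that those counts would show.

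What remains for the active arm is a reporting gap: the logs need not give the reason for a removal after consent.

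**Conclusion.** The point holds for historical controls. The sections disagree on whether an open discretionary exclusion applies to them, and if it does, controls can be passed over and replaced with the outcome in view, in a comparison with neither randomisation nor described blinding.

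Under the assumed shares the effect is modest: a spurious ratio of 1.09 to 1.20, and false positives favouring the model of 4.8% to 7.7% instead of 3.0%. About 3 to 6 skipped charts would be enough. These figures rest on assumed shares, removal of completers only, no true effect and an unmatched z test in place of the clinic-stratified Poisson model in 13.2. The percent form and the amputation endpoint were not quantified.

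Two stronger conclusions do not follow. One is that controls were in fact selected this way; no passage reports any use of exclusion 3. The other is that both arms were trimmed in opposite directions. Under the same method that would give 7.3% at 1 in 10 per arm and 16.3% at 2 in 10, but it requires coordinated removal that nothing in the documents suggests.

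**What to change.** In 8.1.2 and 10.3.1:

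1. State that exclusion 3 does not apply to historical controls and that the explicit list in 10.3.1 governs.
2. Judge control eligibility in reverse date order, using only chart entries dated on or before baseline, before care processes and outcomes are abstracted.
3. Log each control passed over, with the reason.
4. Re-check controls already passed over, and reinstate any dropped only for other reasons who meet the explicit criteria. If there were none, one sentence saying so closes the point.

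For the active arm, where 13.2 says enrolment is finished, report the number, date and reason for any consented patient removed under exclusion 3. Where data and consent allow, add a sensitivity analysis that includes them.

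The cost is a few sentences, a short log and a re-check. The small downside is that a few unusual but eligible control charts stay in the data.
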